[name] will have oversight all activities including the subcontracts. At Brown University, she will oversee all data programming, protocol preparation, data receipt from South Africa, data cleaning, and data analysis. [name] will have oversight over the South African Medical Research Council subcontract activities, in close collaboration with [name]. This includes all primary data collection activities, institutional collaboration for IRB, transfer of data to the USA for cleaning and processing, and translation. Together, Drs. [name] and [name] will ensure adequate systems, training of the study team, enforcement of protocols, working with their experienced institutional financial and grants management teams, to ensure that grant activities are in compliance with US laws, and DHHS and NIH policies, including biosafety, the protection of Human Subjects, data and facilities, as well as parallel applicable laws and policies in South Africa. In the case of unanticipated serious adverse events, and with the permission of children and parents, we will refer to services by tapping into the extensive social service and clinical networks that we have worked with for adolescent health in South Africa including both Drs. [name] and [name]' respective affiliation with the Medical School at University of Cape Town. Project progress will be summarized weekly in order coordinate scientific, fiscal and administrative management of the project, setting priorities for allocation of resources and funds.

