Overview of Randomized Pilot Trial. We will recruit N=282 male adolescents who are the primary targets of the school community-level intervention. We will also recruit N=80 teachers (numbers are average estimates of 40 teachers/school), randomly selecting from a full list of teachers from the school. Data from this pilot trial will help prepare us for a future R01 full-scale efficacy trial that will take the form of a cluster randomized controlled trial where schools will be randomized to an intervention or control arm. In this trial, we will pilot in two schools (School #2 will receive the experimental intervention, and School #3 will serve as a wait-list control). The assignment to the experimental intervention will be randomly determined. For future trial feasibility, the first set of assessments will reflect the outcome questionnaire used at baseline, 1- and 6-months for N=282 boys (Appendix L); we also gather baseline outcomes from N=80 teachers (prior to Teacher Lunch and Learn sessions) and at post-intervention (end of the school year). The teacher instrument is in Appendix M. We will track recruitment and retention strategies and success rates. A second set of assessments for future trial feasibility will evaluate fidelity, ranking integrity and competency of our team's delivery of Teacher Lunch and Learn, Student Intercept activities in real time. These fidelity assessments follow recommendations issued by the Treatment Fidelity Workgroup of the NIH Behavior Change Consortium to ensure rigorous coding of fidelity based on a standardized monitoring checklist (Appendix N).⁷⁶ For acceptability data, we will gather intervention satisfaction forms from male adolescents (Appendix O) and teachers (Appendix P) randomized to the intervention, and gather opinions on content, clarity and appeal of materials, delivery, and format.

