Co-variates: socio-demographics; economic status; household characteristics	
 Items from the South African 2011 Census Questionnaire & World Health Organization Food Security Questionnaire⁹¹ Verbal Autopsy for AIDS orphanhood⁹² 	✓		✓	✓
Mechanisms & Moderators:	
 Norms relating to HIV transmission including condom attitudes, HIV stigma; HIV knowledge; self-efficacy, and skills Resilience; mental health; substance use Sexual aggression norms relating to both HIV transmission and IPV; endorsement rape myths, traditional gender roles; social norms regarding sex and violence 	
 South African HIV Knowledge⁹³; AIDS Related Stigma Scale and Internalized AIDS-Related Stigma Scale^{94,95}; Condom Attitudes Scale - Adolescents⁹⁶; Condom Use Self-Efficacy Scale⁹⁷; Condom-use skills checklist⁹⁸ Connor-Davidson Resilience Scale⁹⁹; Center for Epidemiologic Studies Scale^{100,101}; Alcohol Use Disorders Identification Test¹⁰²; Drug Use Disorders Identification Test¹⁰³ Illinois Rape Myth Acceptance Scale⁸³; Boeringer's Social Norms Measure⁸⁴; Gender Equitable Mens Scale⁸⁵ 	✓	✓	✓

All administration systems (paper forms scanned to digitized data) and data software come with rigorous human Subjects' protections and worked well in our previous collaborative USA-South African trials.

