Analysis and Further Intervention Refinement. We will check all forms for missing data in field and during entry, with at least 2 telephone calls to participants to collect missing data. We will examine key variables for skewness, variability, missing data, and outliers, with transformations to achieve normality if needed. For our acceptability data (satisfaction assessments), we will set 80% reporting positive ratings as a marker of acceptability and examining process data on satisfaction with format, length, etc. For our fidelity data, we will assess fidelity of facilitator implementation, setting 80% as acceptable fidelity, and using data to make final adjustments to training. For our feasibility data, we will also evaluate feasibility in regards to recruitment ease, and retention during outcome timepoints. For trial outcomes, preliminary analyses will include studies of patterns of missing data , dropout rates, and correlations effect size estimates with small samples have large standard errors so we use pilot data to assess hypothesized intervention effects.¹⁰⁴ We will examine key variables for skewness, variability, missing data, and outliers, with transformations to achieve normality if needed. We will examine descriptive statistics for main outcomes and mediators with extreme scores or deviations from normality to be addressed in subsequent analyses. Baseline differences between groups on demographic variables will be examined using t-tests or the Chi-square test, where appropriate, and variables that show differences will be included as covariates in outcome analyses. McNemars test, for paired binary variables, will be used to determine whether the follow-up measurements significantly differ from baseline measurements in the intervention and control arm, separately. Generalized linear mixed (random effects) models, will be used to compare intervention and control group, via treatment by time interaction terms, following intention-to-treat principles. In exploratory analysis, we will look at directions of hypothesized effects. While we are underpowered to test mediation effects directly, we will explore differences between study arms. Effect sizes observed will be used to inform a larger adequately powered RCT. We also examine exposure to other interventions to see how this may be affecting outcomes.

Rigor, Reproducibility, and Transparency

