Aim 3: Pilot Randomized Controlled Trial: In the **Acceptability and Feasibility Aim 3** our primary goal will be to assess acceptability and feasibility of the school community-level preventive intervention, *Schools Championing Safe South Africa*, among **N=282 male adolescents aged 15-17 years** who are the primary targets of the community-level school environment intervention. This sample will be split in a 1:1 ratio (n=141 boys in the intervention school, n=141 boys in the wait-list control school). The goal of this school community-level intervention is to prevent HIV risk, IPV perpetration, and increase bystander behavior) among boys at high risk for HIV and STI risk behaviors and IPV perpetration (e.g., male adolescents aged 15-17 years). In this aim, we will also explore preliminary evidence for hypotheses that the intervention, relative to the control, will produce the following outcomes: (1) reductions in actual or intended HIV risk behaviors; (2) reductions in IPV frequency and decreased endorsement of IPV supportive attitudes; and (3) increased proactive bystander intentions. Outcomes will be collected at baseline, 1- and 6- months. As a secondary aim, we also **survey N=80 teachers** to

assess whether teacher (mis)perceptions have been corrected (e.g., whether teachers perceive student attitudes and behaviors more accurately) and whether they intend to engage in more bystander intervention. Teacher surveys will be collected as baseline (prior to the Teacher Lunch and Learn Sessions) and at follow-up (end of the school year).

Characteristics. We anticipate the following characteristics for study subjects in terms of age and number (see **Table 4**).

Table 4: Anticipated Subject Numbers* and Age

	Adolescents	Total Participants*
Aim 1	Any gender adolescents, ages 12-19	1500
Aim 1	Any gender teachers, ages 18-65	120
Aim 2	Any gender adolescents, ages 12-19*	48
Aim 2	Any gender teachers, ages 18-65*	10
Aim 3	Male adolescents, ages 15-17	282
Aim 3	Any gender teachers, ages 18-65	80

* maximum enrollment targets have been included, final sample sizes will be based on saturation analyses

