The primary objective of this pilot is to test the feasibility and acceptability of the intervention and to generate meaningful effect size estimates for a future fully-powered RCT. We considered sample size needed to demonstrate increased condom use at last sex, reduced sexual violence perpetration, and increased active bystander behavioral intentions. To measure significant change in the three objectives, a total of N=282 adolescent boys will be enrolled, with n=141 in the intervention arm and the same number (n=141) in the control arm. The power calculations described below are based on a McNemar's test for paired proportions, 80% power, and type 1 error rate (alpha) of 5%. These calculations were generated by findings of the R34 testing *Safe South Africa* (R34MH113484-01), which included 80 male adolescents aged 15-17 years. **Condom use:** We assume that in the *Schools Championing Safe South Africa* pilot trial, 88% of male adolescent participants will have ever had sex at baseline, and 63% of those will report at baseline that they used a condom at last sex. **Table 5** shows the sample size required to detect changes between baseline and 6-months in condom use ranging from 3% to 17% at six months at 80% power and a type 1 error rate of 5%. For example, Table 5 shows a sample size in excess of 1000 (N=1138) is required to detect changes in condom usage that are less than 5 percent. To detect larger differences, for example 10% or greater, a maximum sample size of 276 participants is required. To detect changes of 15% or greater in condom use at last sex between baseline and 6 months in the intervention arm, assuming 0.20 correlation between paired observations, 135 adolescent boys are required in the intervention arm. To account for a 3% dropout rate (observed in the *Safe South Africa* study), a total of 141 per arm will be enrolled. **Sexual violence perpetration:** We assume that at baseline, 56% of male adolescent participants will have perpetrated sexual violence in the past 6 months. To detect changes 16% or greater in sexual violence perpetration of sexual violence between baseline and 6 months in the intervention arm, assuming a 0.20 correlation between paired observations, a total of 125 adolescent boys are required in the intervention arm (Table 5). The planned sample size of 141 per arm will account for greater than 3% dropout rate. **Active bystander behavior:** We assume at baseline, 60% of male adolescent participants will have intentions to engage in active bystander behavior. To detect changes 15% or greater in active bystander intentions between baseline and 6 months in the intervention arm, assuming 0.20 correlation between paired observations, a total of 125 adolescent boys are required in the intervention arm (Table 5).

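### Covariates are picked by baseline significance tests with no covariate-by-time term specified, so on the ordinary reading the treatment-by-time comparison stays essentially unadjusted

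*Combined protocol and SAP*

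**What the plan says.** All of the relevant rules are in Specific Aim 3, under Analysis and Further Intervention Refinement.

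- Screening: "Baseline differences between groups on demographic variables will be examined using t-tests or the Chi-square test, where appropriate".
- Inclusion: "variables that show differences will be included as covariates in outcome analyses".
- Arm comparison: "Generalized linear mixed (random effects) models, will be used to compare intervention and control group, via treatment by time interaction terms".

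Table 2 lists the candidate variables as "Co-variates: socio-demographics; economic status; household characteristics" and marks them for collection at baseline, 1 month and 6 months. The outcome schedule for the boys is the same: "Outcomes will be collected at baseline, 1- and 6- months" (Human Subjects Involvement, Aim 3). Each arm is a single school: "School #2 will receive the experimental intervention, and School #3 will serve as a wait-list control" (Overview of Randomized Pilot Trial).

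The document gives no p-value threshold for the screen and no fixed list of covariates. It does not state the form in which a selected covariate enters the model, and it nowhere mentions a covariate-by-time term.

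**The concern.** The comparison of interest is a difference between arms in change over time. A baseline covariate entered in the usual way shifts all three visits of a boy by the same amount, so it adjusts the level of the outcome and not the change. The rule is evidently meant to deal with imbalance between arms, but on that reading it does not act on the term used to compare them.

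With one school per arm, random assignment does not balance the boys' characteristics. The protocol itself links age to the outcomes: in its Significance section, median sexual debut is at 15 and average age at first rape perpetration is 17, and the sample is aged 15 to 17. If the schools differ in age mix, boys could change at different rates over six months for reasons unrelated to the campaign. An estimate labelled as adjusted would still carry that difference. The analysis section says that the observed effect sizes will inform the larger trial.

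**Working it through.** **Planning figure.** The one planning number used below is the sample size, "n=141 in the intervention arm and the same number (n=141) in the control arm" (Statistical design and power). It reproduces. For condom use rising from 0.63 to 0.78 with paired correlation 0.20:

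- covariance = 0.20 × √(0.63 × 0.37 × 0.78 × 0.22) = 0.0400
- discordant cells = 0.63 × 0.22 − 0.0400 = 0.0986 and 0.78 × 0.37 − 0.0400 = 0.2486, which sum to 0.3472
- n = [1.960√0.3472 + 0.842√(0.3472 − 0.15²)]² / 0.15² = 118.7, so 119 boys
- 119 / 0.88 = 135.2 (the plan states 135), and 136 / 0.97 = 140.2, so 141 per arm

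This point does not contest that number.

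**Algebra.** Write the linear model for boy i at visit j as y = β₀ + β₁(time) + β₂(arm) + β₃(arm × time) + γx + u + e, with x fixed at baseline. The change from baseline contains no γx, because x is the same at every visit. With complete data the estimate of β₃ is therefore the same whether or not x is in the model. If x differs between arms by Δ and its effect grows by δ after baseline, β₃ is biased by δΔ. Only an x × time term removes this.

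**Simulation.** From the documents: 141 boys per arm and three visits. Assumed, because the documents give no values: imbalance Δ = 0.5 SD, covariate effect growing by δ = 0.5 per SD after baseline, effect of 0.8 per SD at baseline, random-intercept SD 0.9, no true arm effect. The expected linear bias is 0.5 × 0.5 = 0.25. Mean arm-by-6-month estimates (truth 0) were:

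| Model | No covariate | Main effect | Covariate-by-time |
|---|---|---|---|
| Linear mixed, complete data (15 runs) | 0.242 | 0.242 | −0.020 |
| Logit mixed, complete data (100 runs) | 0.259 | 0.260 | 0.058 |
| Logit mixed, about 20% or slightly more covariate-related loss at 6 months (100 runs) | 0.233 | 0.241 | 0.058 |

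The Monte Carlo standard error of the logit means is about 0.04. In the linear model with complete data, the first two columns agree to about 10⁻¹⁴ in every run. In the logit model, adding the main effect moved the estimate by 0.004 on average with complete data and by about 0.036 with missing visits. In neither case did it reduce the mean bias.

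With δ = 0 and complete data, all three logit estimates were within about 1.2 Monte Carlo standard errors of zero (−0.035, −0.035, −0.046). Imbalance alone, without an effect on change, does not bias the term.

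**Power of the screen.** Assume a two-sided 5% threshold. The standard error of a standardised baseline difference is √(2/141) = 0.119. At a true imbalance of 0.20 SD, power is Φ(0.20/0.119 − 1.96) = Φ(−0.28), about 39%. Power reaches 80% only at 0.119 × (1.960 + 0.842) = 0.33 SD.

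**The case against.** The strongest reply is that the plan never says covariates enter as main effects. That is correct: it is the ordinary reading of the sentence, but an inference. A reader might take the plan to have specified a wrong model, and the text does not support that. It leaves the form open. What stands is that a selection rule is stated and no time interaction is.

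Second, exact invariance needs a linear model, complete data and time-fixed covariates. The sizing outcomes are binary. Condom use applies only to boys who have debuted, so its data are unbalanced even without dropout. Table 2 re-measures the covariates at follow-up. This rules out saying that the covariate cannot move the term. It does not rescue the adjustment: the simulated shifts were small and removed no bias, and the plan selects on baseline values.

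Third, the treatment-by-time contrast already removes stable differences in level between schools. Bias arises only if an imbalanced variable also drives change. A reader might infer that the schools will differ in this way, or that the trial will be biased by the simulated amount. The documents give no such imbalance or slope, and both schools enrol boys aged 15 to 17 from high-prevalence communities.

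Fourth, a reader might add that chance findings in the screen distort the result: 1 − 0.95¹⁰ gives a 40% chance of at least one among ten independent null variables. The documents state neither the number of variables nor a threshold. On the main-effect reading, a covariate picked by chance also barely moves the tested term. Little weight belongs on this.

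Finally, intervention effects are an exploratory secondary aim, and acceptability and fidelity are judged by 80% benchmarks. That limits the severity, although the Assessments section calls the behavioural measures primary outcomes.

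**Conclusion.** The concern holds in a limited form. Covariates are chosen by between-arm tests on baseline demographics, no covariate-by-time term is specified, and the arms are compared through treatment-by-time. On the default reading, the adjustment does not remove confounding of change over time by measured differences between the two schools. This follows from the model structure: it is exact in the linear complete-data case and close to exact with a logit link or missing visits.

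The size of any bias (0.26 on the logit scale in the example) rests wholly on the assumed imbalance and slope. The 39% power figure rests on an assumed 5% threshold.

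A reader might conclude that better adjustment would make the arm comparison sound. It would not: with one school per arm, the intervention and the school cannot be separated by adjusting for the boys' characteristics. The point is a worthwhile correction to an exploratory analysis whose effect sizes are to be carried into a larger trial. It does not affect the feasibility and acceptability objectives.

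**What to change.** Replace the significance-test rule with a short, fixed set of baseline covariates chosen on prognostic grounds from those already collected.

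- Age, and economic status or food security, are suitable examples; Table 2 covers these domains.
- Use sexual debut status only in models that are not restricted to debuted boys. It is constant among boys with a baseline condom-use value.
- Use school grade only if it is confirmed as collected, since Table 2 does not name it.

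Enter each covariate with its interaction with time in the treatment-by-time models, whatever the baseline p-values. Alternatively, compare follow-up values between arms, adjusted for the baseline outcome and these covariates. State which form is used.

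Report baseline differences between the schools descriptively, without tests. Add a sentence that no individual-level adjustment separates the intervention from the school when there is one school per arm.

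The cost is a change of analysis wording and a few degrees of freedom. No new visits are needed, and no new measures unless school grade is wanted and proves not to be collected.

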Goals. In **Acceptability and Feasibility Aim 3** our primary goal will be to assess acceptability and feasibility of the school community-level preventive intervention, *Schools Championing Safe South Africa*, among N=282 male adolescents aged 15-17 years who are the primary targets of the community-level school environment intervention. This sample will be split in a 1:1 ratio (n=141 boys in the intervention school, n=141 boys in the wait-list control school). The goal of this school community-level intervention is to prevent HIV risk, IPV perpetration, and increase bystander behavior) among boys at high risk for HIV and STI risk behaviors and IPV perpetration (e.g., male adolescents aged 15-17 years). In this aim, we will also explore preliminary evidence for hypotheses that the intervention, relative to the control, will produce the following outcomes: (1) reductions in actual or intended HIV risk behaviors; (2) reductions in IPV frequency and decreased endorsement of IPV supportive attitudes; and (3) increased proactive bystander intentions. We also survey N=80 teachers to assess whether teacher (mis)perceptions have been corrected (e.g., whether teachers perceive student attitudes and behaviors more accurately) and whether they intend to engage in more bystander intervention.

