Assessments. Outcome assessments evaluate changes at 1- and 6-months post-intervention, relative to control for these primary outcomes: Do male adolescents report a higher prevalence of condom use at last sex (for those who have debuted) or anticipated risk behaviors (for those who have not debuted) relating to HIV and STI risk acquisition or transmission?; Do male adolescents report fewer experiences of sexual violence perpetration or attempts to perpetrate sexual violence?; and Do male adolescents report increased intentions for active bystander intervention? All measures utilized in the current study are well established, and tested in our prior studies including the complementary *Safe South Africa* trial. We collect self-reported outcome assessments using audio-computer assisted self-interviewing software which limits social desirability bias.⁷⁸ See **Table 2**.

Table 2: Outcome Measures and Satisfaction Assessment					
Outcome	Measures	Baseline	After Intervention	1-month	6-month
Teachers and Adolescent Boys					
Acceptability	Client Satisfaction Questionnaire ⁷⁹		✓		
Teachers					
Teacher intervention for negative adolescent sexual and IPV behaviors	The Perceptions of School Personnel Helping Scale ^{80,81}	✓	✓		
Active Bystander Behaviors	Miller Likelihood to Intervene, Miller Positive and Negative Bystander Behavior ⁸²	✓	✓		
Sexual aggression norms relating to HIV transmission and IPV; endorsement rape myths, traditional gender roles; social norms regarding sex and violence; norms around HIV transmission including condom attitudes, HIV stigma	Illinois Rape Myth Acceptance Scale ⁸³ ; Boeringer's Social Norms Measure ⁸⁴ ; Gender Equitable Mens Scale ⁸⁵ ; AIDS Related Stigma Scale and Internalized AIDS-Related Stigma Scale; Condom Attitudes Scale - Adolescents	✓	✓		
Adolescent Boys					
HIV Risk Behavior & Intentions: HIV and STI status; HIV testing; frequency sex; number and type of partners; use of condoms	• Items taken from South African trials & NIH's Adolescent Medicine Trials Network for HIV/AIDS Interventions	✓		✓	✓
IPV Perpetration Behaviors: type, frequency and severity of IPV; sexual perpetration and aggression, dating violence	• Sexual Experiences Survey Short Form Perpetration ⁸⁶	✓		✓	✓
Bystander Intervention Behaviors: proactive bystander behavior; bystander efficacy and readiness	• Sexual Social Norms Inventory ⁸⁷ • Bystander Behavior Scale ⁸⁸⁻⁹⁰ • Intent to Help Scale ^{88,90} • Bystander Efficacy Scale ^{89,90}	✓		✓	✓

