In the **Refinement Phase (Aim 2)** we showcase drafts of the social norms posters developed by the scientific team during Aim 1 to teachers and students to refine the final messages and visuals to be delivered in the social norms poster campaign. In addition to the social norms posters – which are the foundation to the community-level intervention – we also gather feedback on the other core intervention components (e.g., Teacher Lunch and Learn sessions, Teacher Workbook, and Student Intercept activities) designed to transform poster campaign messages into prevention behaviors. We will gather refinement data using n=5-10 interviews with teachers and k=3-6 focus groups with students. We will implement refinement activities in School #1 (the campaign refinement school) so as not to contaminate the population of teachers and students being targeted in the pilot randomized controlled trial in Aim 3 in Schools #2 and #3. We will use FileMaker Software to pre-program school allocation to the three options (School#1, 2 or 3) using a computerized randomization procedure. This computerized program eliminates any investigator bias in assignment of schools to various conditions.

We will **recruit all teachers in the school for n=5-10 interviews** to further refine our initial poster messages/visuals and the other teacher components (Teacher Lunch and Learn sessions, Teacher workbook to guide classroom intercept activities). Interested teachers will speak privately with the study team to be screened for eligibility. Inclusion criteria includes: (1) any teacher in the school. We will include teachers regardless of what age group they teach but begin sampling with the teachers who teach 15-17 year olds. For teachers interested in participation, our team will then proceed with the consent process. Study staff will provide a signed written informed consent form from each teacher who is eligible and interested in participating for them to review and then schedule an interview time. **Retention of teachers** for follow-up does not apply for these one-time qualitative interviews.

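### With one school per arm, the treatment-by-time test cannot separate the intervention from school-specific change, and its effect size should not power the cluster trial

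*Combined protocol and SAP*

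**What the plan says.** **Analysis.** Under Specific Aim 3, Analysis and Further Intervention Refinement, the arms are compared as follows: "Generalized linear mixed (random effects) models, will be used to compare intervention and control group, via treatment by time interaction terms, following intention-to-treat principles". The level of the random effects is not named. The same paragraph adjusts for demographic variables that differ at baseline, and adds: "We also examine exposure to other interventions to see how this may be affecting outcomes". On later use it says: "Effect sizes observed will be used to inform a larger adequately powered RCT".

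**Allocation.** The Recruitment and retention plan, under Aim 2, states: "We will use FileMaker Software to pre-program school allocation to the three options (School#1, 2 or 3) using a computerized randomization procedure". The Aim 3 Goals paragraph gives the split as "n=141 boys in the intervention school, n=141 boys in the wait-list control school". The school is therefore the allocated unit, with one per arm.

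**Status of the outcomes.** The Assessments paragraph says: "Outcome assessments evaluate changes at 1- and 6-months post-intervention, relative to control for these primary outcomes". The Specific Aims, and the description of Aim 3 data in the human-subjects section, call the same comparisons exploratory and secondary. Both Sample Size and Power sections nevertheless place effect-size estimation for a later, fully powered trial within the primary objective. The Overview of Randomized Pilot Trial says that this later trial "will take the form of a cluster randomized controlled trial where schools will be randomized to an intervention or control arm".

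**What is absent.** Neither the analysis paragraph nor the two power sections (including Table 5) mention clustering, an ICC or a design effect. Nothing in the documents states that arm and school are confounded.

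**The concern.** When each arm is a single school, treatment and school are the same variable. The interaction removes stable differences between the schools. It does not remove a change that happens in one school and not the other between baseline and follow-up, such as a local event, a new programme or a change of staff. The estimate is the intervention effect plus the difference in the two schools' own change, and the data cannot split the two.

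The unspecified random effects do not help. A boy-level effect describes variation between boys only. A school-by-time effect, which is the one needed, cannot be estimated with one school per arm.

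Two things are at stake. A school-specific change could be read as an intervention effect with an interval that is too narrow. That difference could then be carried into the design of a trial that randomises schools, although it is not attributable to the intervention and its precision is unknown.

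**Working it through.** **1. The plan's own figure.** The sample size is for a within-arm McNemar test with two-sided 5% alpha, 80% power and paired correlation 0.20 (Statistical design and power):

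n = [1.96·√pd + 0.8416·√(pd − d²)]² / d², where pd = p₁(1−p₂) + p₂(1−p₁) − 2·0.20·√[p₁(1−p₁)p₂(1−p₂)].

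- Perpetration 0.56 to 0.40: pd = 0.4147, n = 125, as in Table 5.
- Bystander intention 0.60 to 0.75: n = 125, as in Table 5.
- Condom use 0.63 to 0.78: n = 119 sexually active boys; 119/0.88 = 135.2, matching the stated 135. Rounding up to 136, 136/0.97 = 140.2, which rounds up to 141.

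The plan's N is reproduced. It is sized for change within an arm and says nothing about the comparison between arms.

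**2. Degrees of freedom.** 2 schools − 2 arms = 0. Given the two trial schools, there are only two possible allocations, so a school-level randomisation test has a smallest two-sided p of 1.0. More boys, covariates or a school random effect do not alter this.

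**3. Nominal precision.** Boys per school after 3% dropout: 141 × 0.97 ≈ 137. For condom use: 0.88 × 137 ≈ 120. With no true change, the variance of a boy's change is 2p(1−p)(1−0.20).

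- Perpetration (p = 0.56): variance 0.394. SE of the difference in change = √(2 × 0.394/137) = 0.0759. Half-width 1.96 × 0.0759 = 14.9 points.
- Condom use (p = 0.63): variance 0.373. SE = √(2 × 0.373/120) = 0.0788. Half-width 15.5 points.

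**4. What is left out.** The documents give no ICC of change, so a range is assumed. Here the school drift SD is √(ICC × 0.394), the design effect DE is 1 + (m−1)·ICC, true type I error is 2[1 − Φ(1.96/√DE)], and the half-width is 14.9·√DE. The last column repeats the type I calculation with m = 120.

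| Assumed ICC of change | Drift SD, points | DE (m = 137) | Type I, perpetration | Half-width, points | Type I, condom use |
|---|---|---|---|---|---|
| 0.001 | 2.0 | 1.14 | 7% | 15.8 | 6% |
| 0.005 | 4.4 | 1.68 | 13% | 19.3 | 12% |
| 0.01 | 6.3 | 2.36 | 20% | 22.8 | 19% |
| 0.02 | 8.9 | 3.72 | 31% | 28.7 | 29% |

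An ICC of 0.05 would give 48%. It needs a drift SD of 14 points, which nothing in the documents supports, so it is an extreme case only.

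**5. Simulation check.** The setting was one school per arm, baseline 0.56, correlation 0.20, a normal school-by-time shift on the logit scale, a z-test on the difference in change, and 20,000 trials per setting. Logit SDs of 0, 0.1, 0.2, 0.3 and 0.4 correspond to drift SDs of 0, 2.5, 4.9, 7.2 and 9.6 points. They gave 5.3%, 7.8%, 15%, 25% and 34% false positives, in line with the table.

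**The case against.** The strongest reply is that this is a feasibility pilot. Its stated primary goal is acceptability and feasibility, and several sections call the outcome comparisons exploratory. The only numeric benchmarks in the analysis paragraph are the 80% thresholds for acceptability and fidelity, and no go/no-go rule depends on the interaction. The paragraph says the mixed models will compare groups without naming a p-value, and that effect sizes will inform a later trial, not fix its size. The investigators already plan that trial as a cluster design. The inflation rests on assumed ICCs and is slight at 0.001. The calculation uses two time points and a simple test, whereas the plan has three assessments and a covariate-adjusted model. A statement of the confounding, with the model retained, might be enough.

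Much of this is fair. The size of the inflation is not established. A p-value is a reasonable inference from the text, not a quotation. Sizing the next trial on the observed effect is a risk, not a declared method.

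The core stands, however. An exploratory label does not make a standard error valid, and it conflicts with the Assessments paragraph and with the primary objective in the power sections. The analysis paragraph's remark about large standard errors in small samples concerns sampling of boys; the missing component does not shrink with more boys. Demographic adjustment and the look at other interventions may explain part of a difference, but they supply no school-level degrees of freedom.

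It is also true that the separate within-arm McNemar tests are exposed to the same school-specific change. They should be read as tests of change, not of an intervention effect.

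**Conclusion.** The concern holds, and the text should be changed before analysis. That arm and school are inseparable, with zero school-level degrees of freedom, follows from the design alone. The interaction's p-value and interval are valid as treatment inference only if between-school variance of change is exactly zero, and these data cannot test that. The practical size depends on the assumed ICC of change: about 7% to 31% true type I error for perpetration over 0.001 to 0.02, and 6% to 29% for condom use. The acceptability, fidelity, recruitment and retention aims are unaffected, and the N=282 arithmetic is sound for within-arm change.

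**What to change.** **Analysis and Further Intervention Refinement.** Replace the mixed-model sentence with wording such as:

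> The difference between the two schools in change from baseline to 1 and 6 months will be reported descriptively. With one school per arm, arm and school are inseparable, so no p-value or confidence interval will be presented as a treatment effect. Any interval shown will be labelled as reflecting boy-level sampling only, or as a sensitivity range over stated assumed ICCs of change.

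This still permits a fitted model with a boy-level interval, provided it is labelled.

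**Assessments.** Bring the description of these outcomes as primary and compared with control into line with the exploratory status given elsewhere.

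**Both power sections and the closing part of the analysis paragraph.** State that the observed between-arm effect size will not be used to power the cluster trial. That trial should use a minimum important difference and an external range of ICCs. The Aim 1 survey is not a substitute: three schools give only 3 − 1 = 2 degrees of freedom between schools, and a single survey cannot show variation in change.

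**Rationale for N=282.** Keep the number. Describe it as sized for within-arm change, which is not an intervention effect, and for precision in these two schools. By 1.96·√[p(1−p)/n], that precision is about ±8 points on a 56% prevalence (137 boys), ±6.6 on 80% acceptability and ±2.8 on 97% retention (141 boys each). A within-boy correlation of 0.20 would have limits of about 0.03 to 0.36 (Fisher z, n = 137, approximate for binary data).

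**Cost.** No extra schools or boys. The sponsor gives up a between-arm p-value, rewords the effect-size part of the objective and restates the sample-size rationale.
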